# Remote glucose monitoring using the Dexcom G6 Continuous Glucose Monitoring (CGM) System in hospitalized patients with diabetic ketoacidosis (DKA)

Study Purpose and Rationale:

We propose to study use of Continuous Glucose Monitoring (CGM)for glucose monitoring in patients with DKA which would enable the treatment of hemodynamically stable DKA patients outside of intensive care units (ICU) thereby saving ICU beds a precious resource which have become extremely scarce resource during COVID-19 pandemic (1). In most hospitals, protocols for treatment of patients with diabetic ketoacidosis (DKA) require capillary point of care (POC) glucose testing every 1-2 hours (2) . Often, patients need to be transferred to the intensive care units (ICU) for frequent fingerstick glucose monitoring in order to safely administer intravenous insulin to treat the DKA. During the COVID-19 pandemic, this need to transfer patients to the intensive care unit (ICU) for treatment of DKA and the requirement for nurses to enter the room every 1-2 hours has contributed to scarcity of critical care unit beds and shortage personal protective equipment (PPE) Additionally, COVID-19 patients have been prone to develop DKA which has further increased the need for ICU beds (3, 4). Therefore, methods to safely and effective treat patients with DKA outside of ICU setting represent a common and pressing need.

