#### **Prospective Study**

The prospective part of this study will involve recruiting patients in the Emergency Department and offering them the opportunity to use DEXCOM G6 CGM instead of hourly fingerstick point of care glucose testing . We will enroll additional 50 non-critically ill DKA patients who will have glucose levels monitored via DEXCOM CGM and be treated in the stepdown unit. The primary outcome is time to resolution of metabolic acidosis. Secondary outcomes are length of ICU stay, length of hospital stay, frequency of hypoglycemic episodes defined as glucose level <70 mg/dl and cost savings.

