# Statistical Procedures:

The primary outcome for this study is the time to resolution of DKA. We will compare time to resolution of the DKA of patients who had glucose levels monitored via DEXCOM G6 CGM and treated in the stepdown unit (both those enrolled in the retrospective study and those who will be enrolled in the prospective study) to DKA patients who had glucose levels monitored hourly via fingerstick (and not CGM) and treated in the ICU setting.

We will perform a non-inferiority trial to study whether monitoring glucose levels via CGM in DKA patients treated in the stepdown unit is not inferior to DKA treated patients in the ICU setting with hourly fingerstick glucose monitoring.

For a noninferiority trial, based on what we have previously observed for the time to resolution of DKA, and a noninferiority margin of 1/2 the SD, we estimate that a sample size of 98 patients per group will have a 90% power to determine noninferiority at an alpha level of 0.05. Since we enrolled 48 patients in the retrospective part of the study, we will need additional 50 patients enrolled in the prospective part of the study to have 90% power and a noninferiority at an alpha level of 0.05. We plan a conservative approach where we will enroll additional 50 DKA patients who will have glucose levels monitored via CGM. We will compare with the historical control using 1:1 matching, thus will collect historical control data which include DKA patients treated for DKA in the ICU setting with hourly fingerstick glucose monitoring.

We will perform linear regression (for patients enrolled in both retrospective and prospective part of the study) to learn what clinical factors are associated with length of time to the DKA resolution. Then we will use propensity matching for historical control group (DKA patients treated in the ICU setting with glucose levels monitored via hourly fingerstick glucose levels).

To study the frequency of hypoglycemic episodes (<70 mg/dl) in patients from both prospective and retrospective study; we will use CGM glucose data stored manufacture's web based software : Clarity.

We will also evaluate frequency of hypoglycemic episodes (glucose level <70%) in historical control patients who were treated for DKA in the ICU and had hourly glucose level monitoring.

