We will evaluate potential cost savings comparing treatment of DKA patients in the stepdown unit using DEXCOM G6 CGM (both retrospective quality improvement project and prospective study vs treatment of DKA patients in the ICU setting using hourly point of care glucose testing (historical controls). We will include variables such as daily cost of ICU stay vs stepdown unit, cost of DEXCOM CGM.

We will calculate satisfaction scores from nursing surveys for the prospective part of the study.

There are no validated surveys assessing provider satisfaction as use of CGM in the inpatient setting is still a novel approach. We will use a modified CGM survey used for patient/caregivers (11)

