# Study Procedures:

### Retrospective Quality Improvement Project

We will search electronic medical records (EMR) for laboratory data and clinical notes to estimate time to resolution of the DKA. Laboratory data and patient's characteristics which can contribute to time to resolution of DKA will be needed to match historical controls (DKA patients treated in the ICU setting with and glucose levels monitored via hourly fingerstick). All relevant data will be gathered from chart review and stored in Excel format on a secure Department of Surgery server. All statistical analysis will be conducted in cooperation with Center for Innovation and Outcomes Research of the Department of Surgery.

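### Matching variables are tied to time to DKA resolution, yet historical controls also serve hypoglycemia, cost and, by inference, hospital stay, so drivers of those outcomes such as COVID-19 can stay unbalanced

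*Combined protocol and SAP*

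**What the plan says.** **Choice of matching variables.** Statistical Procedures describes a linear regression "for patients enrolled in both retrospective and prospective part of the study", whose purpose is "to learn what clinical factors are associated with length of time to the DKA resolution". The next step is stated as "Then we will use propensity matching for historical control group", and the ratio as "We will compare with the historical control using 1:1 matching". Study Procedures (Retrospective Quality Improvement Project) describes the data to be abstracted in the same terms: "Laboratory data and patient's characteristics which can contribute to time to resolution of DKA will be needed to match historical controls". There is no covariate list, no second selection rule and no balance check.

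**Use of the controls.** Study Design gives time to resolution as the primary outcome and continues: "Secondary outcomes are length of ICU stay, length of hospital stay, frequency of hypoglycemic episodes", with cost savings completing the list. Statistical Procedures evaluates hypoglycemia in the historical ICU patients as well as in the CGM patients. For cost it says "We will evaluate potential cost savings comparing treatment of DKA patients in the stepdown unit using DEXCOM G6 CGM", with historical ICU controls as the comparator. Hospital stay has no analysis paragraph of its own. No separate match or regression adjustment is described for any secondary outcome.

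**COVID-19.** The rationale states that "COVID-19 patients have been prone to develop DKA". Under Study Design, the 48 retrospective CGM patients come from a project that began in January 2021 and stopped enrolling once COVID cases had fallen. The exclusion criteria remove, among others, ventilated patients, those on pressors, those with another reason for ICU care and those with GFR below 30. COVID-19 infection is not an exclusion, a named matching variable or a named data item. The historical controls are given no calendar window.

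**The concern.** Propensity matching balances, at best, the variables placed in the model. A variable chosen because it predicts how fast the acidosis resolves need not predict how long the patient stays in hospital, whether glucose falls below 70 mg/dl, or what the admission costs. A factor that strongly affects those outcomes but is weakly related to resolution time has no stated route into the match. The screening regression is also run in the CGM patients alone (98 planned), so a real driver can be missed by chance.

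COVID-19 illustrates this from the protocol's own account. It is linked there to DKA, and about half of the CGM group was treated during the pandemic. Any control from before the pandemic could not have been infected. A difference in hospital stay or cost would then partly reflect infection rather than the monitoring strategy. These outcomes are secondary, but cost savings is a named outcome and resource use is part of the stated rationale.

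**Working it through.** The plan gives no figure for residual imbalance, so there is none to reproduce. The only plan figures used are the group sizes: 48 retrospective + 50 prospective = 98 CGM patients, and 98 controls. (The 98 itself does not follow from the stated margin, power and alpha, which give 69 per group at one-sided 0.05 or 85 at one-sided 0.025. Nothing below depends on that.)

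**1. Effect on hospital stay through COVID-19**

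Assumed, because the documents give no values:
- share p of the 48 infected: 10-40%
- extra days d per infected patient: 3-5
- no infection among the 50 prospective patients
- share q of controls infected: 0 to begin with

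Shift in the CGM-minus-control mean stay = d × (p × 48/98 − q), with 48/98 = 0.490.
- Low end: 3 × 0.10 × 0.490 = 0.15 days.
- High end: 5 × 0.40 × 0.490 = 0.98 days.
- High end with q = 10%: 5 × (0.196 − 0.10) = 0.48 days.
- High end with q = 19.6%: 0 days.

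The sign is positive: CGM patients appear to stay longer.

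**2. Any omitted factor, in SD units**

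Bias = (difference in prevalence) × (effect in SD). With 98 per group treated as independent, SE = √(2/98) = 0.143 SD. Prevalence differences and effects are assumed.

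| Prevalence difference | Effect (SD) | Bias (SD) | False rejection, nominal two-sided 5% test |
|---|---|---|---|
| 10 points | 0.25 | 0.025 | 5.4% |
| 20 points | 0.5 | 0.10 | 10.8% |
| 30 points | 0.5 | 0.15 | 18.3% |
| 40 points | 1.0 | 0.40 | 80% |

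In step 1 the pooled COVID-19 difference is 0.10 × 0.490 = 4.9 points to 0.40 × 0.490 = 19.6 points. That scenario therefore reaches about the 20-point row and not the last two.

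**3. Does adding the factor to the model help?**

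A simulation of 1:1 nearest-neighbour propensity matching used 98 treated patients, a pool of 400 controls and 400 runs. Assumed prevalence was 30% in CGM patients and 10% in the pool, with an effect of 0.5 SD on stay.

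| Factor in the propensity model | Imbalance after matching | Bias in stay (SD) |
|---|---|---|
| No | 0.196 | 0.11 |
| Yes | 0.005 | 0.006 |

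The Monte Carlo error of each bias is about 0.143/√400 = 0.007 SD. Leaving the factor out keeps essentially the whole 20-point imbalance, and including it removes it. This works only if the pool contains patients with the factor. With none, no covariate choice can produce a match for the infected patients.

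**The case against.** **The plan does not restrict matching to predictors of resolution time.** A reader might infer that only such predictors may be used and that COVID-19 is shut out. The text does not say so. It names one basis for choosing variables and is silent on others. COVID-19 would enter if the regression linked it to resolution time, or if the analyst added it. This stands: imbalance can remain, not must remain.

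**The control window is unknown.** A reader might infer that no match could ever balance COVID-19. That needs controls who all predate the pandemic, and no date is given. Study Design indicates that DKA patients went to the ICU before January 2021 and again after the project stopped, so controls from pandemic months, possibly infected, may be available. This also stands, and is why the window must be stated.

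**Eligibility limits the problem.** Excluding ventilated patients and those with another reason for ICU care removes severe COVID-19, where long stays are most likely. It does not remove or balance milder infection.

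**The direction is not favourable to CGM.** A reader might suspect that the cost case is being inflated. In the worked example the bias lengthens CGM stay, which counts against CGM and could understate savings.

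**Cost need not follow stay.** A reader might scale cost with the extra days. The cost inputs named are daily ICU and stepdown cost and the device, as an open list, and CGM patients later move to a ward. The documents give no basis for proportionality.

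**Some of the comparison is inferred.** The comparator for hospital stay follows from there being one control group and is not stated. For hypoglycemia and cost the text says historical controls without saying whether this is the matched set.

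**Conclusion.** The point holds in this form: the plan ties matching to one outcome, uses historical controls for others without further adjustment, and so can leave drivers of those other outcomes unbalanced. It concerns the secondary comparisons.

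For COVID-19 and hospital stay, the assumed inputs give 0.15 to 0.98 days against CGM, shrinking towards 0 as infected patients appear among the controls. For omitted factors generally, the assumed ranges give anything from a negligible to a serious bias (0.025 to 0.40 SD). None of the prevalences or effects comes from the documents. The effect on cost cannot be sized, and the documents offer neither a mechanism nor a figure for COVID-19 and hypoglycemia. The conclusion rests on the gap in the covariate rule rather than on any one of these numbers.

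**What to change.** Before control data are extracted, amend Statistical Procedures as follows.

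1. List the propensity covariates in advance. Besides predictors of resolution time, include COVID-19 status and baseline admission factors for stay, hypoglycemia and cost: comorbid conditions, GFR within the eligible range and diabetes type. Keep them in whatever their association with resolution time.
2. State the calendar window of the historical controls.
3. State that the matched controls are the comparator for hospital stay, hypoglycemia and cost, if that is the intention.
4. Report standardized differences after matching and adjust the secondary comparisons for residual imbalance.
5. If COVID-positive CGM patients have no COVID-positive control, restrict the stay and cost comparisons to COVID-negative patients and describe the others separately.

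The cost is SAP wording, a few more fields in a chart review already planned, and a somewhat smaller secondary comparison if step 5 applies. Because step 5 covers only stay and cost, it does not reduce the primary comparison. Regression adjustment or calendar matching could serve the same end; what matters is that the choice is fixed in advance.

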Continuous glucose monitoring (CGM) is widely used in the outpatient setting but its use is still investigational in the inpatient setting. Several studies showed improvement in detection of hyperglycemic and hypoglycemic episodes with the use of CGM when compared to fingerstick point of care (POC) glucose testing in both the ICU and non-ICU setting (5-8). The FDA has allowed use of DEXCOM G6 CGM in hospitalized patients during the COVID-19 pandemic (9). In a recent pilot study performed during the COVID-19 pandemic done in hospitalized patients in the perioperative period, DEXCOM G6 CGM showed a mean absolute relative difference (MARD) of 9.4% compared to point of care (POC) glucose measurements (10). Use of continuous glucose monitoring has not been reported in hospitalized patients with DKA. The DEXCOM G6 CGM (https://www.DEXCOM G6.com/) provides glucose levels in real time, as well as glucose trends, and alarms if glucose levels are in hypoglycemic or hyperglycemic range. These safety features can decrease the risk of hypoglycemia when patients with DKA are being treated with insulin infusion. Furthermore, the DEXCOM G6 CGM is labeled as an "integrated continuous glucose monitoring system" which can reliably and securely transmit glucose data to digital devices allowing remote monitoring of glucose levels by multiple care team members without entering patient's room and thus reducing the number of healthcare contact and use of personal protective equipment (PPE). If CGM is shown to be non-inferior to fingerstick glucose monitoring (measured by time to resolve DKA, incidence of hypoglycemia) in patients with DKA, then hemodynamically stable non-intubated DKA patients would not have to be transferred to the ICU for frequent fingerstick glucose testing as is now being done. Instead, these patients could be treated and monitored with CGM on the stepdown unit. This would help reallocate critical care unit beds, save time and effort for the nurses and help conserve PPE.

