### Study Design:

#### Retrospective Quality Improvement Data

In January 2021 during COVID 19 pandemic, we launched a quality improvement project with goal to treat non-critically ill DKA patients outside of ICU setting in order to reallocate ICU beds for critically ill patients at New York Presbyterian Hospital /Columbia University Irving Medical Center. Before this quality improvement project, DKA patients were treated in the ICU setting because the DKA protocol requires hourly fingerstick glucose monitoring, which is considered higher level of care and not appropriate for stepdown unit or medical/surgical wards. During this quality improvement project, we monitored glucose levels remotely with continuous glucose monitoring (CGM) device DEXCOM G6 thus eliminating the need for hourly fingerstick glucose testing. Therefore, patients with DKA whose glucose levels have been monitored via DEXCOM G6 CGM have been treated in the stepdown unit instead of the ICU setting where glucose levels are monitoring hourly via fingerstick point of care glucose testing. We enrolled 48 patients (with additional 2 patients who had glucose levels monitored with CGM but were treated in the ICU setting therefore will not be used for this analysis).

Study participants were not being recruited and asked for their participation; non-critically ill DKA patients who presented in DKA had glucose levels monitored via CGM. Given that the recommended hourly fingerstick checks needed for treatment could not be performed on the stepdown unit and only in the ICU, the Dexcom G6 CGM device eliminated the need for hourly fingerstick checks and thus removed the barrier for patients being admitted to stepdown. Once the number of COVID cases decreased and ICU beds were more readily available, the hospital returned to practicing the pre-COVID standard of care, which was admitting DKA patient to the ICU for hourly glucose monitoring and we stopped enrolling patients for this retrospective quality improvement project

We propose to study outcomes of DKA patients who had glucose levels monitored with DEXCOM G6 CGM treated in the stepdown unit. The primary outcome is time to resolution of metabolic acidosis. Secondary outcomes are length of ICU stay, length of hospital stay, frequency of hypoglycemic episodes defined as glucose level <70 mg/dl and cost savings

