# Inclusion Criteria:

age >18, AG>20 (normal is 5-17) with bicarbonate <19 (normal is 19-27), positive urine ketones or beta hydroxybutyrate >0.3 (normal is <0.27)

glucose level >250 mg/dl on presentation to the ED

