In order to have glucose levels sent from the transmitter to the DEXCOM app, each patient needs to have a user name and a password. A user name and password for each patient is created by the research team. Patient's information is coded when transmitted to these phones, meaning that instead of referencing any PHI such as MRN to identify the patient, the patient is labeled via a unique study-specific identifier ("study participate 001"). If the phones were to get lost, there will be no concern for improper release of PHI. The "study smartphone for the patient " is placed on the IV pole next to insulin infusion bag.

2. A study coordinator will set app DEXCOM follow apps (which are necessary for glucose to be sent from the patient study phone) on the study smartphones given to the nurse and provider for remote glucose monitoring.

There is a 2 hour "warm up" period until glucose levels are transmitted the study patient smartphone and during that time glucose levels should be checked via hourly fingerstick as per the DKA protocol.

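### Hypoglycemia is counted from a continuous sensor trace in CGM patients but rests on hourly fingersticks in controls, with no common sampling basis, window or denominator

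*Combined protocol and SAP*

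**What the plan says.** Statistical Procedures (combined protocol and SAP) gives the source for both the retrospective and the prospective CGM patients: "we will use CGM glucose data stored manufacture's web based software : Clarity". It adds that the frequency will also be evaluated in "historical control patients who were treated for DKA in the ICU and had hourly glucose level monitoring". The comparison group is described in the same section as having "glucose levels monitored hourly via fingerstick (and not CGM) and treated in the ICU setting". The threshold is 70 mg/dl throughout, apart from an evident slip in the control sentence, where the unit is printed as a percent sign.

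Study Purpose and Rationale describes non-inferiority as "measured by time to resolve DKA, incidence of hypoglycemia". It also cites studies in which CGM detected hypoglycemic episodes better than fingersticks did.

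Study Procedures, Prospective Study, describes the sensor record:

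- There is a 2-hour warm-up without CGM values, and "during that time glucose levels should be checked via hourly fingerstick as per the DKA protocol" (item 2).
- Staff act on hourly CGM readings, and a fingerstick is taken when the CGM value is below 100 mg/dl (item 3).
- The sensor comes off on transfer to the ICU (item 3) and before MRI or CT (item 4).
- The sensor may stay on after DKA resolves, but the phones are returned at resolution (item 6).

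None of these sections states a common sampling interval, a common start and end of counting, or a denominator.

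**The concern.** A trace that records continuously can show a short low that falls between two hourly fingersticks. If both groups had the same true hypoglycemia, the plan's two sources could still return different frequencies. The protocol's own rationale says that the methods differ in detection.

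Hypoglycemia is the safety half of the case for treating these patients outside the ICU. Without a rule set in advance, a higher CGM count could be real harm or only denser sampling, and a real excess could be explained away as sampling. Conversely, parts of the prospective stay are missing from the trace, so a low CGM count is not plainly reassuring either. The choice of how to count would fall after the data are seen.

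**Working it through.** The plan gives no rate, margin or sample size for hypoglycemia, so it has no figure of its own to reproduce. What follows is illustrative. The only inputs from the documents are the hourly control schedule, the 98 per group (48 + 50 CGM patients, matched 1:1), and the 9.4% MARD. Durations and rates of lows are assumed.

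**1. Counts.** Assume a low of D minutes starting at random relative to an exact hourly check, full detection by CGM, and equal duration in both groups. The hourly check catches a share min(1, D/60), so the CGM-to-control ratio is 60/D for D up to 60.

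| D (min) | Caught hourly | Ratio | Share CGM would have to miss to cancel, 1 − D/60 |
|---|---|---|---|
| 15 | 25% | 4.0 | 75% |
| 30 | 50% | 2.0 | 50% |
| 45 | 75% | 1.33 | 25% |
| 60 or more | 100% | 1.0 | 0% |

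**2. Patients with any recorded low.** With a Poisson mean of m true lows per patient, the CGM group shows 1 − exp(−m) and controls show 1 − exp(−m·D/60). For m = 0.2 and D = 30 this is 1 − exp(−0.2) = 18.1% against 1 − exp(−0.1) = 9.5%. That is 98 × 0.181 = 17.8 against 98 × 0.095 = 9.3 patients, a false gap of 8.6 points. Over m from 0.1 to 0.4 and D from 15 to 45, the gap runs from 2.3 points (m = 0.1, D = 45) to 23.5 points (m = 0.4, D = 15).

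**3. Forces in the other direction.** In the prospective part the trace lacks the warm-up and any time after removal for ICU transfer or imaging. These losses lower the CGM count by an unknown amount. Device handling for the 48 retrospective patients is not described. Sensor error can add or miss lows: the rationale cites a "mean absolute relative difference (MARD) of 9.4% compared to point of care (POC) glucose measurements", which would be 0.094 × 70 = 6.6 mg/dl at the threshold if that perioperative figure held there.

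**4. Which measure survives missing hours.** Put both groups on an hourly grid, with all CGM hours filled and a share p of control hours filled at random.

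- *Low readings per filled hour.* The expected low readings per low are D/60 in CGM patients and p·D/60 in controls. Dividing the latter by p restores D/60, so the ratio is 1.0 at any D.
- *Merged episodes per filled hour* (adjacent lows, or lows separated only by a missing hour, count once). A low spanning k grid hours is seen in controls with probability 1 − (1 − p)^k, so the ratio is p / [1 − (1 − p)^k]. For 120 min, k = 2 and the ratio is 1/(2 − p). For 90 min, k is 1 or 2 with equal chance and the ratio is 1/(1.5 − 0.5p). For 180 min, k = 3.

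| Control hours filled | 90 min | 120 min | 180 min |
|---|---|---|---|
| 87% | 0.94 | 0.89 | 0.87 |
| 50% | 0.80 | 0.67 | 0.57 |

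A simulation of 200,000 lows per setting (24-hour window, tolerance ±15 min) agrees closely. At 50% fill it gives 0.80, 0.68 and 0.58, and low readings per filled hour stay at 0.98 to 1.00.

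- *Proportion with any low.* For rare lows shorter than an hour the ratio is about 1/p: 1/0.87 = 1.15 and 1/0.50 = 2.0. It therefore needs the fill rate reported beside it.

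**5. Off-hour fingersticks.** If checks prompted by the CGM alert capture a share f of the lows that the grid misses, the ratio becomes 1 + f(60/D − 1). At f = 0.5 that is 2.5, 1.5 and 1.17 for 15, 30 and 45 min. Using them would bring back the imbalance.

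**The case against.** The strongest reply is about weight. This is a secondary outcome, the plan says it will be evaluated rather than tested, no margin is attached, and the primary outcome does not depend on it. All of that stands and limits the severity. It does not remove the point, because the rationale places incidence of hypoglycemia beside time to resolution as a measure of non-inferiority.

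The ratios also need lows shorter than an hour and equal duration in both groups. The documents support neither assumption. CGM patients have an alert below 100 mg/dl, and if early detection shortens lows in that group, control lows last longer and the ratio moves toward 1.0. The figures show what could happen, not what will.

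Three stronger readings are tempting, and the documents do not support them.

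- A reader might infer that the CGM count must be biased upward. Denser sampling pushes that way, but the lost trace pushes back by an unknown amount.
- A reader might infer that the warm-up loss is negligible, because eligibility requires "glucose level >250 mg/dl on presentation to the ED" and reaching 70 within 2 hours needs a fall of (250 − 70)/2 = 90 mg/dl per hour. But warm-up starts at sensor placement, which follows staff agreement and written consent. No limit is set on the delay from presentation.
- A reader might infer that the controls have no count source. The natural reading is charted hourly fingersticks: the control sentence refers to hourly monitoring, and Study Procedures takes data from chart review.

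**Conclusion.** The point holds, as a matter that should be fixed before analysis. The plan takes the two groups' hypoglycemia frequencies from sources with different sampling and sets no common window or denominator, so the contrast is not comparable as written. The possible distortion from sampling alone runs from none (lows of an hour or more) to a fourfold count ratio (15-minute lows), given equal true rates, equal durations, exact hourly control checks and full CGM detection. Lost trace in the prospective part works against this, and sensor error can work either way. The net direction and size are not determined by the documents. A reader might infer that the trial's main non-inferiority conclusion is compromised. It is not, since time to DKA resolution does not use these counts.

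**What to change.** Add a short rule to Statistical Procedures for the between-group comparison.

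- **Window.** Use the same one in both groups: insulin start to DKA resolution as defined for the primary outcome, including time after ICU transfer. The laboratory criteria for resolution are not stated and must be set first.
- **Sampling.** Use an hourly basis in both groups. In CGM patients take the Clarity value nearest each scheduled hour, or a charted scheduled fingerstick where no CGM value exists. In controls take the charted hourly fingerstick. Fix one tolerance in advance, for example ±15 min, and leave unfilled hours missing. Do not use alert-triggered off-hour fingersticks, because controls had no such trigger.
- **Measures.** Make readings below 70 mg/dl per filled hour the main measure. Do not use merged episodes per filled hour: when lows last over an hour and control hours are missing, that measure makes the CGM group look safer. Report the proportion of patients with any low beside it, with the share of hours filled, for the 48, the 50 and pooled.
- **Full trace.** Report the complete Clarity record as a description of the CGM group only.

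The cost is SAP wording, abstraction of fingersticks and alignment of clock times. Short lows seen only by CGM leave the comparison, and sensor-versus-fingerstick error remains. Charts of the 48 may hold few fingersticks to fill gaps, since in that project "the Dexcom G6 CGM device eliminated the need for hourly fingerstick checks".
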